3.1 Study Periods

The ARC004 study consists of 4 study periods:

- Initial Escalation - Group 1 only
- Up-dosing - Group 1 or Repeat Up-dosing for subjects switching to a daily AR101 dosing regimen (Section 3) at a study site that has not yet received approval to enroll these subjects in ARC008

- Maintenance - Group 1 and subjects switching to a daily AR101 dosing regimen and who completed Repeat Up-dosing at a study site that has not yet received approval to enroll these subjects in ARC008
- Extended Maintenance - Groups 1 and 2

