3.1.3 Repeat Up-dosing (Subjects Switching to Daily Dosing)

If a subject meets the criteria for switching to AR101 daily dosing and is at a study site that has not yet received approval to enroll these subjects in ARC008, the subject may begin daily dosing and have visits in Repeat Up-dosing in ARC004 until they can enroll in ARC008 ([Section 3](#)). If ARC008 is available, the subjects will complete an Exit/Early Discontinuation visit in ARC004 and enroll in ARC008.

Subjects entering the Repeat Up-dosing Period will start with a daily dose of either 80, 120, or 160 mg at the discretion of the investigator. The dose will be increased every 2 weeks as per [Table 3](#), until the subject reaches the target dose of 300 mg daily.

To escalate to the next dose, subjects must be tolerating the current dose. Some subjects may require de-escalation, and once the lower dose is tolerated they may again attempt to proceed with up-dosing. To allow for a personalized titration of dosing, the Repeat Up-dosing Period will last for a maximum of 26 weeks. Subjects who are not able to achieve the target dose of

300 mg/day and tolerate that dose level within 26 weeks will be discontinued from AR101 dosing and complete an Early Discontinuation Visit; these subjects will not be eligible to participate in ARC008.

Subjects who reach the target maintenance dose of 300 mg and maintain this dose for at least 2 weeks (maximum duration of Repeat Up-dosing of 26 weeks) will exit ARC004 and enter ARC008 when it is available. If ARC008 is not available at the time the subject expects to exit ARC004, subjects will continue daily dosing and have visits in ARC004 until ARC008 is available, then continue dosing in ARC008.

Table 3: Repeat Up-dosing Schedule (Subjects Switching to Daily Dosing)

Repeat Up-dosing Schedule (Subjects Switching to Daily Dosing)	
Investigational Product Dose, mg ^a	Interval (weeks)
80	2
120	2
160	2
200	2
240	2
300	2

^a All mg doses shown refer to milligrams of peanut protein.

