6.3.10 Exit Visit/Early Discontinuation Visit

Subjects who tolerate their EM regimen and complete the EM phase will have an Exit Visit, including an Exit DBPCFC, per [Figure 1](#) and the Schedule of Events ([Appendix 1](#)).

Subjects who fail initial escalation or up-dosing, or who prematurely discontinue treatment at any other time during the study, will return to the site for an Early Discontinuation Visit that consists of the same procedures as the Exit Visit, but without a DBPCFC. The Early Discontinuation Visit is to occur 14 days after the last dose of study product for those subjects who will permanently discontinue AR101 treatment.

Subjects who have the option to switch to AR101 daily in ARC008 ([Section 3](#)) have 2 options to continue, depending on whether ARC008 is available at their study site. If ARC008 is available, subjects will complete an ARC004 Early Discontinuation Visit without a DBPCFC and enroll in ARC008 where they will undergo Repeat Up-dosing. If ARC008 is not available at the study site, subjects may start AR101 daily dosing and have visits in ARC004 until ARC008 is available, then continue dosing in ARC008.

Once ARC008 is available at the study site, subjects will have their Early Discontinuation Visit within 3 days following their last dose of AR101 in ARC004. The exit DBPCFC will be omitted.

Subjects who withdraw from ARC004 wholly or in part due to intolerable GI symptoms, who are not enrolled in the optional saliva study, may be approached at the time of their Early Discontinuation Visit to provide voluntary consent to enroll and participate in the saliva sub-study. If this occurs, such subjects will provide a saliva sample as part of the Early Discontinuation Visit and then again during post-OIT follow-up (table in [Appendix 6](#)).

The following procedures will be performed at the Exit/Early Discontinuation Visit:

- Concomitant medication review.
- Diet (food allergen) history.
- Completion of the food allergy related quality of life questionnaire (FAQLQ), and the food allergy independent measure (FAIM) questionnaire after the completion of the Exit DBPCFC.
- Completion of the Treatment Satisfaction Questionnaire for Medication (TSQM-9) and the exit questionnaire after the completion of the Exit DBPCFC.
- Assessment of asthma control in asthmatic subjects using the Asthma Control Test questionnaire.
- Complete (not just symptom-directed) physical examination, including height and weight.

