7.8.2 Individual Stopping Rules

Individuals may stop the study at any time by withdrawing their consent if they experience subjectively intolerable AEs, dosing symptoms, or for any other reason. Because ARC004 is exploring alternative dosing schedules, the approach to individual stopping rules caused by dose-related AEs varies by regimen. All subjects discontinuing the study early and permanently discontinuing AR101 treatment will return to the CRC for an Early Discontinuation Visit no later than 14 days after the last AR101 exposure.

QD Dosing Regimens

When on QD dosing regimens (including Up-dosing and Maintenance for Group 1, and QD EM for both Groups, as applicable), 7 or more consecutive days of missed daily dosing due to non-compliance constitutes an individual stopping rule. During Up-dosing, Group 1 subjects must halt up-dosing and re-start with a reduced dose if more than 4 days of dosing are missed. Missing 3 or more consecutive days on 3 occasions while on daily dosing in any period is an individual stopping rule, as is missing 15 or more consecutive days of QD dosing for any reason.

QOD, BIW, QW, or QOW Regimens

Any subject receiving nondaily dosing (QOD, BIW, QW, or QOW) who has 1 related SAE; 1 related AE graded severe; 2 related AEs occurring on separate occasions, both graded moderate; or 3 consecutive doses judged “not tolerated” will be considered as a treatment failure and discontinued from ARC004 for safety reasons. Such subjects may be eligible to enroll in ARC008 and receive AR101 daily in the Repeat Up-dosing period. If ARC008 is not available, the subjects will begin daily dosing and have visits in the Repeat Up-dosing period in ARC004. Once the subject reaches the target dose of 300 mg daily and maintains that dose for 2 weeks, that subject will be able to continue this dose regimen until ARC008 is available.

Occurrence of any of the following will result in the cessation of dosing and the subject being discontinued from the study as an escalation failure nonresponder:

- Failure to accomplish up-dosing of study product after 3 attempts
- Failure to identify a tolerated dose of study product after 3 attempts at dose reduction

Finally, administration of 3 or more doses of epinephrine for the treatment of any dose-related allergic reaction in any subject during any period is an individual stopping rule.

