9.2 Study Endpoints

9.2.1 Primary Endpoint

The primary endpoint is the frequency of treatment-related AEs, including SAEs, during the overall study period (from enrollment to the end of EM).

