3. ENDPOINTS

3.1. PRIMARY ENDPOINT

The primary endpoint is the frequency of treatment-related AEs, including SAEs, during the overall study period (from enrollment to discontinuation/exit). ARC004 is specifically designed to begin exploring alternate (eg, nondaily) oral immunotherapy (OIT) extended maintenance dosing regimens. The data generated for alternative dosing regimens in ARC004 are expected to be exploratory and hypothesis-generating.

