- Group 2 combined cohorts B and C: QD, QOD, BIW, and Overall
- Group 2 Overall QD

Sponsor: Aimmune Therapeutics, Inc.

Protocol: ARC0004

Version: Version 1.0, 10Jul2019

For subjects in Group 2 who were not able to tolerate BIW or QOD dosing per study design and who subsequently reverted to a QD regimen, safety events for these subjects while on QD will be flagged in listings. Safety data collected after the dosing change will not be summarized in tables but will be presented in separate listings for key safety endpoints.

No summaries for any QW or QOW dosing regimens will be tabulated since no subjects initiated these dosing regimens.

All relevant data collected in the database and any derived data will be included in data listings and unless otherwise noted sorted by age group, group/cohort, subject number, test/measurement, and visit and time point as appropriate.

All statistical methods will be based on the International Conference on Harmonization (ICH)-E9 Guidance for Industry "Statistical Principles for Clinical Trials".

A review of the database will be conducted before database lock. Any decision to amend the planned statistical analysis will be documented in an amendment to the statistical analysis plan and details will be included in the CSR.

If the assumptions underlying the formal statistical methods proposed are not met during the analysis of the final data, an alternative, more appropriate, statistical method will be used and any changes documented in the statistical methods section of the CSR, including the rationale for use.

Additional exploratory analyses of the data will be conducted as deemed appropriate.

These analyses will be fully documented and clearly identified as post-hoc and exploratory.

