11. CHANGE FROM ANALYSIS PLANNED IN PROTOCOL

The analysis methods and summaries detailed in the SAP include, but are not limited to, all analyses included in the Statistical Considerations section of the protocol, with the following exceptions:

- Baseline for DBPCFC is defined as the Exit food challenge from ARC003 for both Group 1 and Group 2 subjects.
- For secondary endpoints relating to post-maintenance DBPCFC, only Group 1 post-maintenance DBPCFC results will be summarized. Group 2 Exit ARC003 food challenge data will not be summarized in ARC004 as post-maintenance.
- Post-maintenance DBPCFC as referenced in the protocol will be referred to as maintenance DBPCFC in this document and all corresponding outputs.

Any deviations from the plans detailed in this SAP will be described and justified in the final clinical study report. A separate document to this SAP will provide a table of contents and mockups for the expected layout and titles of the TLFs. Any changes to format, layout, titles, numbering, or any other minor deviation will not necessitate a revision to the SAP nor will it be considered a deviation from planned analyses. Only true differences in the analysis methods or data handling will necessitate such documentation.

Sponsor: Aimmune Therapeutics, Inc.

Protocol: ARC0004

Version: Version 1.0, 10Jul2019

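### SAP 6.1 keeps safety data after reversion to daily AR101 out of every table, although SAP 3.1 runs the primary endpoint to discontinuation or exit; the QD dates in SAP 10.1 also need correcting

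*SAP*

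**What the plan says.** SAP 6.1 covers Group 2 subjects who could not tolerate QOD or BIW and reverted to QD. Their events on QD are flagged in listings, and "Safety data collected after the dosing change will not be summarized in tables". Separate listings are promised for key safety endpoints.

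SAP 3.1 defines the primary endpoint as the frequency of treatment-related AEs "during the overall study period (from enrollment to discontinuation/exit"). Protocol 9.2.1 has the same endpoint "during the overall study period (from enrollment to the end of EM"). SAP 11 says that the SAP covers "all analyses included in the Statistical Considerations section of the protocol, with the following exceptions". It then lists three exceptions, all about the food challenge: its baseline, the restriction of post-maintenance summaries to Group 1, and a change of name.

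On conduct, Protocol 7.8.2 says that if ARC008 is not available, "the subjects will begin daily dosing and have visits in the Repeat Up-dosing period in ARC004". Protocol 3.1.3 adds that "the Repeat Up-dosing Period will last for a maximum of 26 weeks". Protocol 3.1 lists "Repeat Up-dosing for subjects switching to a daily AR101 dosing regimen" as a study period distinct from EM. Under Protocol 6.3.10, once ARC008 opens at the site, "subjects will have their Early Discontinuation Visit within 3 days following their last dose of AR101 in ARC004".

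SAP 10.1 dates the QD period of Cohorts 1, 3A, 3B and 3C from the first to the last QD day in ARC004, and computes duration as last dose minus first dose plus one.

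**The concern.** A reverter at a site without ARC008 goes on taking AR101 inside ARC004, under re-escalation, after having shown intolerance of the nondaily regimen. That time falls before discontinuation, so it lies inside the SAP 3.1 window. Under 6.1 nothing that happens in it reaches a table.

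SAP 3.2 makes anaphylaxis, epinephrine use and AEs leading to withdrawal of AR101 secondary endpoints. A subject who cannot complete Repeat Up-dosing is taken off AR101 (Protocol 3.1.3), and that can only happen after reversion. An AE behind such a withdrawal would therefore be missing from the tabulated endpoint.

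Two further gaps affect the programming. SAP 7.5 ends EM at the last dose before the Exit DBPCFC, which Protocol 6.3.7 omits for these subjects, so they have no defined EM end. And 6.1 names only intolerant subjects. Those who switch to daily dosing after missed or withheld doses (Protocol 3) can enter the same Repeat Up-dosing, with no stated rule.

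**Working it through.** The plan gives no figure for this rule. Its only ARC004 sample-size figure reproduces and is unaffected: 1 − 0.996^400 = 0.799, against the stated 80%.

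**1. Windows**

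| Source | Primary window ends at | Repeat Up-dosing in ARC004 |
|---|---|---|
| Protocol 9.2.1 | end of EM | outside (a separate period in Protocol 3.1) |
| SAP 3.1 | discontinuation/exit | inside (the visit follows the last ARC004 dose, Protocol 6.3.10) |
| SAP 6.1 | dosing change, for tables | excluded |

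So 6.1 agrees with the protocol window and disagrees with SAP 3.1. The passage that moved is 3.1, and section 11 does not declare it.

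**2. Incidence.** Planned sizes from Protocol 7.8.3: Cohort 2 = 50; Cohort 3 = 175 over three arms, so 3B + 3C = 2 × 175/3 = 116.7. One subject whose first SAE, anaphylaxis or epinephrine use follows reversion lowers that row by:
- Cohort 2: 1/50 = 2.0 percentage points
- 3B/3C: 1/116.7 = 0.9 percentage points

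This holds however person-time is cut. Tables restricted to ages 4–17 have smaller denominators and larger steps. For any treatment-related AE the change is small, because an intolerant reverter is normally already counted for the triggering reaction.

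**3. Rates, only if person-time runs to the last ARC004 dose.** Let r be the share reverting, g the QOD + BIW weeks before reversion (4 or 28), and w the daily weeks after it: 8 (160, 200, 240 and 300 mg at 2 weeks each) or 26 (the maximum). The 10% for r is an assumption; the documents give no number. With equal event rates in all weeks, Cohort 2 Overall is shown at N/(N + rw) of the true rate, where N = (1 − r) × 28 + rg.
- r = 10%, w = 26: 25.6/28.2 = 0.908 (g = 4); 28/30.6 = 0.915 (g = 28)
- r = 10%, w = 8: 25.6/26.4 = 0.970; 28/28.8 = 0.972
- Person-time cut at the dosing change: 1

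**4. QD span in SAP 10.1.** A 3B/3C reverter has 28 QD weeks, then g nondaily weeks, then w daily weeks. Actual QD time is 28 + w; first-to-last-day duration is 28 + g + w. Mean per 3B/3C subject at r = 10%:
- g = 28, w = 26: span 28 + 0.1 × 54 = 33.4 weeks; actual QD 28 + 2.6 = 30.6; inflation 33.4/30.6 = 1.09
- g = 4, w = 8: span 28 + 0.1 × 12 = 29.2; actual QD 28.8; inflation 1.01

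If the post-reversion events are also left out while the whole span stays in the denominator, the first case gives a QD rate of 28/33.4 = 0.838 of the true one.

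**The case against.** The best reply on the window is that Protocol 7.8.2 describes these subjects as treatment failures discontinued from ARC004, so their later data would fall after discontinuation and outside SAP 3.1. That does not stand. The same section gives them daily dosing and visits in ARC004, and Protocol 6.3.10 puts the Early Discontinuation Visit after the last of those doses.

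On rates, a reader might infer that the SAP drops events, keeps the person-time and so understates exposure-adjusted rates, or that it gives no common cut-off at all. The documents do not support either as the natural reading. The 6.1 rule is about safety data, and SAP 10 counts extent of exposure within safety, with Study Treatment Exposure as its first subsection. SAP 10.3 divides by subject-years in the study period, and the event-table periods in 6.1 include no Repeat Up-dosing. The 10.1 QD row gives Cohort 2 no QD period. All of this fits stopping person-time with the events. What remains is that no sentence says so, while SAP 7.5 also defines an active treatment period that runs to the last ARC004 dose.

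It is also fair that nothing is concealed: 6.1 states the exclusion, and SAP 10.3 lists serious events, anaphylactic reactions and AEs leading to discontinuation. The study is descriptive, and Protocol 3.1.5 expects most Repeat Up-dosing to take place in ARC008. These points limit the size; they do not reconcile 6.1 with 3.1.

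**Conclusion.** The concern holds in a limited form. SAP 6.1 and SAP 3.1 cannot both be followed for reverters who stay in ARC004, and the change of window from the protocol is undeclared. Listings alone would carry later treatment-related events and any first SAE, anaphylaxis, epinephrine use or AE-related withdrawal after reversion. Each such first event is worth 2.0 points in Cohort 2 or 0.9 points in 3B/3C at planned, all-age sizes.

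The number affected is not given and is probably small. Incidence of any treatment-related AE hardly moves, so a material distortion of that headline figure should not be inferred. Understated rates are a risk only under the person-time reading in step 3, with ratios that rest on an assumed 10% reverting.

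The QD-span error in 10.1 is separate and comes from that section's own wording. It would disappear if 6.1 were taken to remove exposure after the dosing change as well, but 10.1 does not say that.

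**What to change.** 1. Tabulate post-reversion events in a separate column, QD after reversion, with its own subject-years, and count them in the overall primary-endpoint summary. If the exclusion is kept instead, restate SAP 3.1 as on-regimen to the end of EM, matching Protocol 9.2.1.
2. In SAP 10.1, end the initial QD period at the last QD dose before the first QOD dose. For subjects without an Exit DBPCFC, end EM at the last QOD/BIW dose (SAP 7.5).
3. State in SAP 10.3 that events and subject-years use the same dates, and apply the same rule to subjects who switch to daily dosing after missed doses.

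Cost: SAP wording, plus one column from data already collected for the listings. The safety figures become slightly less favourable and the overall summary takes in re-escalation exposure, which the separate column makes visible. Keeping the exclusion and restating 3.1 needs wording only.

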6.2. STRATA AND COVARIATES

No statistical modeling will be performed for this study, and no stratification was applied to the group or cohort assignments in this open-label, follow-on study.

6.3. SUBGROUP ANALYSES

In general, summaries of the primary and secondary endpoints will be presented for the children aged 4-17 years. Additionally, key safety tables will be presented for 18-55 year old subjects.

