1.3 Rationale for the Current Study

ARC004 is designed as a follow-on study of ARC003. The study population will therefore be based on the ARC003 study population: approximately 500 international peanut-allergic children and adults (ages 4 to 55 years, inclusive). Three main considerations inform the design of the current study ARC004. The first is to allow placebo-treated subjects from ARC003 to have the opportunity to access active treatment with AR101. The second is to prolong treatment periods with AR101 in order to continue assessment of its safety and efficacy profile. Finally, ARC004 is specifically designed to begin exploring alternate (eg, nondaily) OIT extended maintenance dosing regimens. Because no previous peanut OIT studies have formally examined nondaily dosing intervals, no published preliminary data exist to provide guidance. Therefore, the data generated in ARC004 are expected to be exploratory and hypothesis-generating, and to have the potential to shape a larger subsequent study to confirm the observations made in ARC004 of nondaily dosing regimens.

The rationale for extending the interval between OIT doses is primarily derived from the roughly 100 years of accumulated clinical expertise with subcutaneous immunotherapy (SCIT), as encoded in the current SCIT practice parameter documents ([Cox et al, 2011](#)). Patients taking SCIT for environmental and/or Hymenoptera venom allergies are conventionally started on schedules that begin, in the up-dosing phase, with doses administered once or twice per week, or in some cases even more frequently (eg, “rush” or “cluster” immunotherapy). As patients become hyposensitized and achieve their target maintenance dose, the intervals between injections are then lengthened to monthly during the maintenance period, with no loss of clinical efficacy or increase in AEs. In turn, this conventional monthly maintenance schedule lessens the substantial logistical and economic burdens on patients and families and helps to ensure long-term adherence. While adherence to therapy is important in all disease contexts, it is especially critical in immunotherapy, a modality that requires periodic antigen administration over the span of years to reprogram immune responses and clinically improve chronic conditions.

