9.1 Analysis Populations

The primary population of analysis for all analyses will be the Safety population. The Safety population will consist of all subjects who receive study treatment during ARC004.

A Per Protocol (PP) population, limited to subjects who have no major protocol deviations and who undergo Exit DBPCFC, may be defined. Exclusions will be determined by data review and documented before database lock.

Additional analysis populations may be defined in the SAP.

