4.1. SAFETY POPULATION

The primary population of analysis for all analyses will be the Safety population. The Safety population will consist of all subjects who receive at least one dose of study treatment during ARC004.

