9. EFFICACY

9.1. ANALYSIS OF EFFICACY SECONDARY ENDPOINTS

To confirm the efficacy of AR101 through reduction in clinical reactivity as measured in a DBPCFC to a cumulative dose of 4043 mg, the Exit food challenge will be summarized by group/cohort (Group 1, Group 2 Cohort 1, Group 2 Cohort 2, Group 2 Cohort 3A, Group 2 Cohort 3B, and Group 2 Cohort 3C). For Group 1, the maintenance DBPCFC will be summarized separately. Non-food-challenge efficacy endpoints also will be summarized by group/cohort (Group 1, Group 2 Cohort 1, Group 2 Cohort 2, Group 2 Cohort 3A, Group 2 Cohort 3B, and Group 2 Cohort 3C). Except where otherwise noted, DBPCFC summaries will be included for the completer population for age group 4-17 years.

The study examines DBPCFC changes from the baseline of study ARC004 (i.e. DBPCFC completed at end of study ARC003) to the end of study ARC004.

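### All treated subjects are declared the primary population, but the SAP tabulates primary and secondary endpoints in general only for ages 4-17 and does not list this as a change from the protocol

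*SAP*

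**What the plan says.** Protocol 9.1 defines the set without an age limit: "The Safety population will consist of all subjects who receive study treatment during ARC004". SAP 4.1 keeps that definition ("The Safety population will consist of all subjects who receive at least one dose of study treatment during ARC004") and repeats the protocol's rule on its use: "The primary population of analysis for all analyses will be the Safety population". Protocol 1.3 gives the study age range as 4 to 55 years.

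SAP 6.3 then states that, in general, "summaries of the primary and secondary endpoints will be presented for the children aged 4-17 years". It adds that adults aged 18-55 will get key safety tables, which it does not name. Section 10 repeats both statements for safety data. For the food challenge, SAP 9.1 says that, unless otherwise noted, "DBPCFC summaries will be included for the completer population for age group 4-17 years".

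SAP 10.3 names two AE tables that will also be produced for ages 18-55: the overall AE summary and the SAE summary.

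SAP Section 11 says that the SAP covers all analyses in the protocol's statistical section, apart from a short list of exceptions. There are three: the food-challenge baseline, not reporting the Group 2 ARC003 exit challenge as post-maintenance, and the renaming of the post-maintenance challenge. Age is not among them.

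**The concern.** The declared population and the tabulated one differ. The primary endpoint in protocol 9.2.1 and SAP 3.1 is the frequency of treatment-related AEs, including SAEs, and the rule is to analyse it in all treated subjects. SAP 6.3 is headed as a subgroup section, yet no all-ages endpoint table is specified of which ages 4-17 would be a subgroup. Section 9 of the protocol summarises by group, cohort and phase and has no age restriction.

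Three things are at stake. First, the study report may not contain the treatment-related AE profile, or the desensitization rates, in the population that the plan calls primary. Second, a reader of Section 11 would conclude that nothing about the population had changed. Third, the denominators are ambiguous. SAP 6.1 and 10.14 summarise events and anaphylactic reactions in the Safety population, and 10.3 sets its 5% cut-off for frequent events on the Safety population, while Section 10 limits safety tables in general to ages 4-17. Two programmers could follow this text and produce different tables.

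**Working it through.** The point is mainly textual, so the passages are set side by side first. The one figure that might seem to be affected is checked last.

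**1. AE tables (SAP 10.3).** The section bullets 15 table types. An adult version is named for 2, the overall summary and the SAE summary, which leaves 15 − 2 = 13 with none stated. Four of those 13 are specific to treatment-related AEs: by SOC/PT, exposure-adjusted rates for the frequent ones, grade 3 or higher, and hypersensitivity. These are the detailed displays of the primary endpoint.

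**2. Food-challenge efficacy tables (SAP 9.1.1 to 9.1.4).** These cover response rates, maximum tolerated dose, maximum symptom severity and epinephrine use at the challenge. Section 9.1 sets ages 4-17 and allows noted exceptions, but none of the four subsections notes one.

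**3. Other secondary endpoints.** The pattern recurs.
- SAP 9.1.7 defines domains and scoring for the adult FAQLQ form but tabulates only the child, teen and parent forms. FAIM is tabulated for ages 4-17.
- In 9.1.8 the TSQM-9 scale scores are for ages 4-17. The exit survey is summarised for the Safety population with no local age limit.
- In 10.11 the ACT is analysed for ages 4-11 and 12-17.

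**4. Where adults remain.** Disposition (8.1), demographics and baseline (8.3) and exposure (10.1) are given for both age groups. Listings cover all enrolled subjects (7.2).

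**5. The sample-size figure.** Protocol 9.4 and SAP 2.4 state an 80% probability of observing at least one AE with about 400 treated subjects and a background rate of 4 per 1,000.
- Reproduction: 1 − (1 − 0.004)^400 = 1 − 0.996^400 = 79.9%. This agrees with the stated 80%.
- Effect of splitting by age: the documents give no adult share, so assume 10%, that is 360 aged 4-17 and 40 adults. The probability of at least one event is 1 − 0.996^360 = 76.4% in the younger group and 1 − 0.996^40 = 14.8% in adults. For the two together it is 1 − (1 − 0.764)(1 − 0.148) = 79.9%.
- With an assumed 15% (340 and 60) the parts are 74.4% and 21.4%, and the total is again 79.9%.

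The figure depends on how many subjects are treated and observed, not on which tables they enter. Adult events are still collected and listed, so an age filter on tables leaves it unchanged.

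**The case against.** The case for leaving the plan alone has four parts.

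- **The restriction is not absolute.** SAP 6.3 and 10 both say that it holds in general, the adult key safety tables are an open list, and the table shells are in a separate document. More adult tables than the two named may therefore exist. This stands: the SAP does not rule them out, but it does not commit to them either.
- **The headline primary result may exist for adults.** A reader might infer that the primary endpoint is not produced for adults at all. The documents do not support that. The overall AE summary reports counts, subject incidence and exposure-adjusted rates for events meeting criteria that are not spelled out. If relatedness to treatment is one of them, the top-line figure is available in both age groups and the counts could be added. What has no stated adult or all-ages version is the breakdown by SOC/PT and the separate treatment-related rate tables.
- **Adult results by regimen would be thin.** This also stands. At an assumed adult share of 5% to 15% of about 400, there are 20 to 60 adults over six group/cohort columns, on average about 3 to 10 each. With the Clopper-Pearson intervals planned in SAP 9.1.1, even 3 responders of 3 gives a lower limit of 0.025^(1/3) = 29%, and 10 of 10 gives 0.025^(1/10) = 69%. This argues against reading much into an adult-only column. It does not argue against an all-ages table.
- **The protocol leaves detail to the SAP.** Protocol Section 9 defers full methodology to the SAP, 9.1 allows further populations to be defined there, and the study is descriptive with no formal comparisons. Showing ages 4-17 as the main display is therefore a legitimate choice. But the SAP repeats the all-treated rule instead of replacing it, and its own list of changes is silent.

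**Conclusion.** The mismatch holds. Both documents declare all treated subjects primary for all analyses. The SAP as written specifies no all-ages table for the primary endpoint and no Section 9.1 food-challenge efficacy table that includes adults, and it does not declare this in Section 11. In size, 13 of the 15 AE table types in SAP 10.3 have no stated adult or all-ages version, and neither does any of the four sets of food-challenge efficacy summaries. The number of subjects affected cannot be stated, because the documents do not give the adult share.

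Two stronger readings should be avoided. A reader might infer that adults are dropped from the analysis, but they stay in the Safety population, in disposition, demographics, exposure and listings, and in at least two AE tables. A reader might also infer that the 80% probability of observing an AE falls; it does not. No hypothesis test is affected. This is a defect of reporting and disclosure that should be corrected before database lock. The conclusion rests on the SAP text, since the table shells were not available.

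**What to change.** 1. Add all-ages versions, on the full Safety population, of the treatment-related AE tables (by SOC/PT and by exposure-adjusted rate) and of the SAE table.
2. Add an all-ages Exit DBPCFC response table on the full Completer population.
3. Keep 4-17 and 18-55 as subgroup displays of these tables, so that the 4-17 tables already planned are not lost.
4. In SAP 6.3 and 10, name the adult key safety tables, and state whether the overall AE summary includes relatedness to treatment.
5. If 4-17 stays the main display, list it in Section 11 with the reason. State which denominator applies in 10.14 and for the 5% cut-off in 10.3.

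The cost is small: existing programs rerun without the age filter, a few repeated tables, and short text edits. The drawback is sparse adult counts per cohort in the 18-55 displays, which should be presented as descriptive only.
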